Visit 3-Final Assessment visit: Medical history and concomitant medications collection, formal drug interaction assessment, vital signs, orthostatic blood pressures, complete physical exam and detailed neurological exam, and all efficacy and safety assessments are repeated that were done in the screening, baseline and 20 mg/kg/day assessment visit, except for the cannabis, drug, alcohol and tobacco abuse questionnaire. Adverse event check is done. Subjects will take the study drug upon their arrival to the clinic and record the time. On the morning of the visit, subjects will collect their urine and bring it to the visit. Study coordinator will collect and store the urine cups in a -80°C freezer until shipment. Blood draw is performed 3 hours after the dose is taken, for cannabis testing and safety labs. Subjects will be monitored and vital signs and orthostatic blood pressures will be checked at 1 and 3 hours after taking the study drug. Returned study drug is counted. Compliance will be checked by study drug count and cannabis analysis testing. Home diary is collected and reviewed.

Visit 4-Safety follow up: Concomitant medications, formal drug interaction assessment, vital signs, orthostatic blood pressures, history & complete physical examination, MDS UPDRS, H&Y rating, UDysRS, MoCA, QUIP-RS, C-SSRS, NPI, SCOPA-sleep, RBDSQ, Anxiety short form, Depression short form, Emotional and behavioral dyscontrol short form, Fatigue Severity Scale, Pain Intensity and Interference short form, IRLS, adverse event check, blood cannabis lab testing and urine pregnancy test (women childbearing potential). Safety labs and EKG will be done if there was a clinically significant change at the assessment visit compared to baseline visit. The PI will evaluate the subject for signs of withdrawal.

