25 mg/kg/day). During phone calls subjects are monitored for adverse events, as well as changes in medical history and concomitant medications. Subjects are also called 3 days after stopping the study drug to check for signs of withdrawal. Further, in case CBD alters the reliability of self - report, repeated measures will be taken of a set of tests three times: at baseline, low dose and high dose. During the 10 days that subjects are on a low dose the measurements will be taken on the 3rd and 9th day by phone and at the visit on the 10th to 15th day. During the 28 days on high dose the measurements will be taken on the 12th and 22nd day by phone and at the visit on the 28th +/- 4 days. The phone assessments include the primary outcome (assessment of tolerability) and symptoms of hepatotoxicity, SCOPA-sleep, Anxiety short form, Depression short form, Emotional and behavioral dyscontrol short form, and EQ-5D-5L. At low dose visit (end of 10 days on 5 mg/kg/day), each 20 mg/kg/day visit and each end of treatment phase assessment visits, urinary CBD and metabolites will be tested. To increase compliance with taking study drug, subjects will be asked to fill out a diary at home. The diary will be a record of the date and time subjects take study drug, adverse and beneficial events, and whether they talked to study staff on phone that day, and if so what they were told to do with the dose. Study drug is dispensed at the baseline visit and at the start of the second 7-week treatment phase visit so that subject has enough to take until they return for the low dose visit. At that visit they are given enough to last through 20 mg/kg/day. At the 20 mg/kg/day visit they are given enough for the time on 25/mg/kg/day. As in Stage 1, the purpose of the visit at 20 mg/kg/day is to limit the amount of study drug that is dispensed at any one time and facilitate compliance, safety and drug control. In the instance that a subject does not reach the 20 mg/kg/day dose, due to intolerance, then they will come in when and if they need more study drug to complete 10-15 days on their maximal tolerated dose. If they have enough to last through the 10-15 days then they return for the Final Assessment visit, and therefore have fewer total visits.

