#### Procedures at each visit

Visit 1- Screening visit: Consent, demographics, concomitant medications, formal drug interaction assessment, family medical history, medical history & physical examination (complete physical exam and

detailed neurological exam), vital signs, orthostatic blood pressures, tremor evaluation, MDS-UPDRS III, H&Y rating, MOCA, Drug, alcohol and tobacco abuse screening test, safety assessments (as listed in section IV A, except for RBDSQ, IRLS, PDQ-39 and EQ-5D), EKG and safety labs (as in dose escalation study), blood cannabis analysis testing, serum pregnancy test (for women childbearing potential) and inclusion/exclusion criteria are done. Study subjects are instructed not to take cannabis from outside source throughout the study.

Visit 2- Baseline visit: Eligibility confirmation (including tremor evaluation), medical history, concomitant medications collection, formal drug interaction assessment, vital signs, orthostatic blood pressures, brief physical exam, MoCA, MDS-UPDRS, H&Y rating, UDysRS, RPW, cognitive assessment battery (including tests of verbal intellectual function, attention, processing speed, executive function, verbal learning and memory, visuospatial memory, speeded verbal fluency and word retrieval), RBDSQ, C-SSRS, IRLS, PDQ-39, EQ-5D, urine drug (THC) test (urine dipstick test), urine pregnancy test (women childbearing potential) and study drug dispensing is done and, if appropriate, randomization. Home diary is also dispensed. Subjects take the first dose and are instructed on how to take the medication and how to fill out the diary at home. Subjects will be monitored and vital signs and orthostatic blood pressures will be checked at 1 hour after taking the study drug. Subjects are also told to bring in empty, partially used and unused bottles of study drug at next clinical visit. Subjects will be told not to take the study drug on the day of the next visit, as they will take it upon arrival under instruction by study staff. Subjects will be given two urine cups, 100 mL each, and will be instructed to collect their urine the morning of the low dose visit. They are asked to fill each cup at least 3/4 full, if possible and to bring them to the visit (no refrigeration needed).

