Visit 3 and Visit 7-Low dose visit (end of 10 days on 5 mg/kg/day): On the morning of the visit, subjects will collect their urine and bring it to the visit. Study coordinator will collect and store the urine cups in a -80°C freezer until shipment. Concomitant medications, formal drug interaction assessment, change in medical history, vital signs, orthostatic blood pressures, brief physical exam, MDS-UPDRS, UDysRS, H&Y rating, RPW, Anxiety short form, Depression short form, Emotional and behavioral dyscontrol short form, Fatigue Severity Scale, Pain Intensity and Interference short form, MoCA, RBDSQ, QUIP-RS, C-SSRS, NPI, SCOPA-sleep, IRLS, EQ-5D, PDQ-39, CGI, PGI, and urine pregnancy test are done. Study drug compliance check, adverse event check and blinding assessment are done. Subjects will take their study drug upon their arrival to the clinic and record the taking time. Blood is drawn for cannabis testing and safety labs 3 hours after the dose. Subjects will be monitored and vital signs and orthostatic blood pressures will be checked at 1 and 3 hours after taking the study drug. Home diary is collected and reviewed. The next study drug supply and home diary are dispensed. Subjects are instructed on how to fill out the diary at home and are told to bring in empty, partially used and unused bottles of study drug at next clinical visit. Subjects will again be given urine cups and instructions.

Visit 4 and Visit 8-20 mg/kg/day Assessment visit: Subjects will be on 20 mg/kg/day for 5 days. They will come back to clinic on either day from 2nd through 5th day while on 20 mg/kg/day. On the morning of the visit, subjects will collect their urine and bring it to the visit. Study coordinator will collect and store the urine cups in a -80°C freezer until shipment. Medical history and concomitant medications collection, formal drug interaction assessment, vital signs, orthostatic blood pressures, brief physical exam, CGI, PGI, and adverse event (including SCOPA-Sleep and C-SSRS) check are done. Blood is drawn for complete metabolic profile. Study drug is collected and counted. Study drug is dispensed: and subject is instructed in how to take it. Home diary is collected and reviewed. The next home diary is dispensed. Subjects will be told not to take the study drug on the day of the next visit, as they will take it upon arrival under instruction by study staff. Subjects will again be given urine cups and instructions.

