Visit 5-End of first 7-week (47 days) and Visit 9-second 7-week (115 days) treatment phase assessment visits: Same procedures are conducted as at the previous low dose visit, except for study drug and home diary dispensation. In addition, complete physical exam, detailed neurological exam, blood draw, urinalysis, ECG, and full cognitive assessment battery are done. Subjects will take their study drug upon their arrival to the

clinic and record the taking time. Blood is drawn for cannabis testing and safety labs 3 hours after the dose. Subjects will be monitored and vital signs and orthostatic blood pressures will be checked at 1 and 3 hours after taking the study drug.

Visit 6-Start of second 7-week treatment phase: Study drug and home diary dispensation and instruction will be performed. Formal drug interaction assessment will be done. Subjects take the first dose of study drug. Subjects will be monitored and vital signs and orthostatic blood pressure will be taken at 1 hour after taking the study drug. Subjects are also told to take study drug and record the taking time upon their arrival to clinic on the next clinical visit day.

Visit 10-Safety follow up: Vital signs, orthostatic blood pressures, history & complete physical examination, concomitant medications collection, formal drug interaction assessment, MDS-UPDRS, H&Y rating, UDysRS, RPW, MoCA, RBDSQ, QUIP-RS, C-SSRS, NPI, SCOPA-sleep, Anxiety short form, Depression short form, Emotional and behavioral dyscontrol short form, Fatigue Severity Scale, Pain Intensity and Interference short form, IRLS, PDQ-39, EQ-5D-5L, adverse event check, urine pregnancy test and cannabis lab testing are done. Hematology, complete metabolic profile, urinalysis and EKG will be done if there was a clinically significant change at the high dose evaluation visit compared to baseline visit. The PI will evaluate the subject for signs of withdrawal.

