#### **C.4 Study Drug: Epidiolex:**

Purified CBD from GW is a strawberry flavored liquid, in sesame oil, provided as 100 mg/ml, extracted from high CBD plant material. The placebo is the same, but without CBD. The study drug is best taken fasted, as food will increase Cmax and delay Tmax. The study drug could be taken with a small amount of food as needed if the subjects experience nausea. It is to be taken twice daily at a standard time, minimum of 6 hours apart. Subjects are instructed to take it before breakfast (30 to 60 minutes) and the same before dinner. Further detail is proprietary. Subjects are instructed not to drink grapefruit for 7 days prior to the first dose of study medication and during the rest of the study (both Stages).

The study drug is taken as normal on the mornings of assessments. As far as practical, the same assessor carries out assessments at each visit. Assessment data are stored and not made available at subsequent visits.

Subjects take their routine anti-PD medication on the day of clinical visit, and when ON (PD medications are working) the testing is done.

CBD and metabolite levels will be measurements:

- In Stage 1, blood CBD and metabolite levels will be measured at the screening visit, final assessment visit and safety follow up visit. Urinary CBD and metabolites levels will be tested at the final assessment visit.
- In Stage 2, blood CBD and metabolite levels will be measured at screening visit, baseline, low dose visit (end of 10 days on 5 mg/kg/day) and end of each treatment phase assessment visits. Urinary CBD and metabolites levels will be tested at the low dose visit, 20 mg/kg/day visit and the end of each treatment phase assessment visit.

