Appendix A Schedule of events Stage 1 Open label dose escalation tolerability study												
	Screening	Baseline	Treatment Period							Safety Followup		
Week		1	1-4							4	5-6	6
day	< negative 21	1	1-3	4-6	7-11	12-16	17-19	20-25	26-31 (k)	27-29	30-39	40 (+/- 4)
Clinic visit	1	2							3			4
Telephone call*			1	2	3	4	5	6 (h)		7(i)	8(h)	
Dosage of CBD or placebo mg/kg	0	5(take the first dose in clinic)	5	7.5	10	15	20	20	20 (take the study drug prior to clinic visit)	0	0	0
Informed consent	√											
Eligibility Criteria	√	√										
Demographics	√											
Medical History (a)	√											
Family medical history	√											
Medical History - interval	√	√	√	√	√	√	√		√	√		√
Concomitant Medications	√	√	√	√	√	√	√		√	√		√
Study drug compliance check									√			
Dispense study drug and instruction		√										
Adverse Events (b)			√	√	√	√	√		√	√		√
Formal drug interaction assessment	√	√							√			√
Vital Signs(c)	√	√ (l)							√ (n)			√
Orthostatic Blood Pressures check	√	√ (l)							√ (n)			√
Height and Weight	√	√							√			√
Complete Physical Exam (d)	√								√			√
Neurological exam	√								√			
Brief physical exam (heart and lung auscultation)		√										
Hematology (e)	√								√			√ (j)
Hemoglobin A1C	√											
Complete metabolic profile (f)	√								√			√ (j)
Blood cannabis analysis	√								√ (m)			√
Urinalysis (g)	√								√			√ (j)
Urine Drug (THC) test		√										
Urine CBD and metabolites levels test (o)									√			
Urine cups dispense and urine collection instruction		√										
ECG (12-LEAD)	√								√			√ (j)
Serum Pregnancy Test (for women childbearing potential)	√											
Urine Pregnancy Test (for women childbearing potential)		√							√			√
Assessment of past marijuana use	√											
Drug, alcohol and tobacco abuse screening test	√											
MOCA	√								√			√
MDS-UPDRS part III	√											
MDS-UPDRS		√							√			√
Unified Dyskinesia Rating Scale (UDysRS)		√							√			√
H & Y rating	√								√			√
QUIP-RS	√								√			√
C-SSRS	√	√							√			√
NPI	√								√			√
SCOPA-sleep	√		√	√	√	√	√		√	√		√
RBDSQ		√							√			√
IRLS		√							√			√
Anxiety short form	√								√			√
Depression short form	√								√			√
Emotional behavioral dyscontrol short form	√								√			√
Fatigue severity scale	√								√			√
Pain intensity and interference short form	√								√			√
CGI									√			
PGI									√			
Home diary dispense & instruction		√										
Home diary collection & review									√			

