g. Urinalysis will be performed locally using sponsor-supplied dipsticks, including leukocytes, specific gravity, pH, protein, ketones, glucose, nitrite, blood, urobilinogen, and bilirubin. If nitrite, blood, or protein tests are positive, a microscopic examination will be performed at the central laboratory.
h. Call patient to remind them the clinical visit next day
i. Call patient to collect adverse events and information of signs of withdrawal
j. Hematology, chemistry, urinalysis and EKG will be done if there was a clinically significant change at the end of study visit compared to baseline visit.
k. For some patients, the visit can occur during 10-15 days on max dose, not just on the 10th day.
l. Subject will be monitored and vital signs will be checked at before and 1 hour after taking the study drug.
m. Blood draw will be performed 3 hours after taking the study drug of the clinical visit day.
n. Subject will be monitored and vital signs will be checked at before and 1 and 3 hours after taking the study drug.
o. Clean catch urine collection after taking the study drug. Urine is collected in a 500 mL container and stored in 3-4 samll cups (120 mL, fill up to 3/4).

# Schedule of Event—Stage 2

Appendix B schedule of event Stage 2 RCT		schedule of events																															
week (number of days)	screening	baseline		Treatment Period														Washout			Treatment Period										Safety Followup		
		1	1-3	4-9	1-7 (47 days)														7 to 10 (21 days)			10 to 17 (47 days)										17	17 to 19 (10 days)
Days	<negative 21	1	1-3	4-9	10 (+5) (k)	11-13	14-16	17-21	22-24	25-34	35-44	45-48	49 (+/- 4) (l)	50-52	53-69	70	71	71-73	75-79	80 (+5) (k)	81-83	84-86	87-91	92-94	95-104	105-114	115-118	119 (+/- 4) (l)	120-122	123-132	133 (+/- 4)		
Dosage of CBD or placebo mg/kg	0	5 (take the first dose in clinic)	5	5	5 (take the study drug prior to clinic visit)	10	15	20	25	25	25	25	25 (take the study drug prior to clinic visit)	0	0	0	5	5	5	5 (take the study drug prior to clinic visit)	10	15	20	25	25	25	25	25 (take the study drug prior to clinic visit)	0	0	0		
Clinical visit*	1	2		3			4						5			6			7			8					9				10		
Telephone call**			1	2 (l)		3	4 (q)		5	6	7	8 (i)		9 (j)		10 (i)		11	12 (i)		13	14 (q)		15	16	17	18 (i)		19 (i)	20 (j)			
Informed consent	✓																																
Eligibility Criteria	✓	✓																															
Demographics	✓																																
Medical History (a)	✓																																

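### The dosage rows of both schedules place the dose before five visits at which the visit text has it taken on arrival and the schedule notes require a pre-dose check

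*Combined protocol and SAP*

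**What the plan says.** **Schedules (Appendix 1).** The Stage 1 dosage row marks Visit 3 "20 (take the study drug prior to clinic visit". The Stage 2 dosage row marks Visits 5 and 9 "25 (take the study drug prior to clinic visit" and uses the same parenthesis, at 5 mg/kg, for Visits 3 and 7.

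**Visit text (C.2 and C.3, Procedures at each visit).** For Stage 1 Visit 3: "Subjects will take the study drug upon their arrival to the clinic and record the time". For Stage 2 Visits 3 and 7, and again for Visits 5 and 9: "Subjects will take their study drug upon their arrival to the clinic and record the taking time".

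**Instructions given to subjects.** At both baseline visits and at Stage 2 Visits 4 and 8: "Subjects will be told not to take the study drug on the day of the next visit". At Visit 6, looking ahead to Visit 7: "Subjects are also told to take study drug and record the taking time upon their arrival to clinic on the next clinical visit day".

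**Schedule notes.** Stage 1 note n and Stage 2 note p call for vital signs before the dose and 1 and 3 hours after it. Stage 1 note m and Stage 2 note o put the blood draw 3 hours after that day's dose.

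**Section C.4.** "The study drug is taken as normal on the mornings of assessments". The sentence names no visit and does not say where the dose is taken.

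**The concern.** A coordinator working from the schedule would have the subject dose before coming in. One working from the visit text would give the dose in clinic. Section C.1 sends readers to Appendix 1 for further detail on the design, and no rule says which text prevails.

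If the dosage row is followed, three things suffer:

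- The pre-dose vital signs and orthostatic pressures can no longer be taken in clinic.
- The 1-hour check may already be past, depending on how long before arrival the dose was taken.
- The 3-hour draw, which supplies the CBD level and the safety labs, rests on a dose time that nobody at the site observed.

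Vital signs, orthostatic pressures and labs are one of the four components of the primary safety outcome in section IV.A for both stages. Section C.4 also relies on CBD concentrations to monitor subjects taking CYP3A4 or 2C19 inhibitors, so mixed dosing practice would make those levels harder to compare.

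**Working it through.** The plan gives no figure to reproduce here. The check sets the sources side by side and counts visits.

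**Step 1. The five visits.**

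| Visit | Dosage row | Visit text | Vital-signs note | What the subject is told beforehand |
|---|---|---|---|---|
| Stage 1 Visit 3 | before the visit | on arrival | Stage 1 note n | at baseline: do not dose that day |
| Stage 2 Visit 3 | before the visit | on arrival | Stage 2 note p | at baseline: do not dose that day |
| Stage 2 Visit 5 | before the visit | on arrival | Stage 2 note p | at Visit 4: do not dose that day |
| Stage 2 Visit 7 | before the visit | on arrival | Stage 2 note p | at Visit 6: dose on arrival |
| Stage 2 Visit 9 | before the visit | on arrival | Stage 2 note p | at Visit 8: do not dose that day |

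These are all the visits with 1- and 3-hour checks. Stage 2 note n is a different note: it covers baseline and Visit 6, where the first dose is given in clinic and nothing conflicts. A few Stage 2 vital-sign cells appear to carry the letter g in the copy reviewed. Note g is serum chemistry, so these are read as p.

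**Step 2. Could the parenthesis mean in clinic, before the assessments?** That is hard to sustain. In both rows the baseline cell says explicitly that the dose is given in clinic, so the row itself separates the two situations.

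**Step 3. Where does the pre-dose check come from?** Only from notes n and p. The visit text asks for the 1- and 3-hour checks and does not mention a pre-dose one. The dosage row therefore contradicts the visit text on where the dose is taken, and contradicts the notes on whether a pre-dose reading can be made in clinic.

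**Step 4. Planned visits carrying the conflict.** Inputs are 10 and 50 completers, with recruitment of up to 20 and 60 (C.1), and 48 in Stage 2 (Sample Size Justification). Stage 1 has one such visit per subject, on open-label drug. Stage 2 has four, two in each treatment phase, so two are on CBD and two on placebo.

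- 10 + 50 completers: 10 × 1 + 50 × 4 = 210, of which 10 + 50 × 2 = 110 on active drug.
- 10 + 48: 10 + 48 × 4 = 202, of which 10 + 48 × 2 = 106 on active drug.
- Upper bound if every recruit attended every visit: 20 + 60 × 4 = 260, of which 20 + 60 × 2 = 140 on active drug.

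**Step 5. Visits at which the pre-dose reading is lost.** The share of subjects who would dose at home is not in the documents. For assumed shares of 0%, 10%, 50% and 100%, the losses are 0, 21, 105 and 210 of 210 visits, or 0, 11, 55 and 110 of the 110 on active drug. Visits are counted rather than readings because note c in both schedules says blood pressure is measured once on each day assessed, which leaves the intended number of readings unclear. Missed 1-hour checks are not counted, because no lead time is given.

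**The case against.** The strongest reply is that the text staff work from already settles the matter. All five visit narratives say on arrival, every instruction staff are told to give agrees with them, and nothing directs staff to tell a subject to dose at home. That largely stands, and it is why the number affected may be small. The Visit 6 wording is adequate for Visit 7.

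One narrow gap remains. For Visits 5 and 9 the instruction is given at Visits 4 and 8. Under C.3, subjects who do not reach 20 mg/kg/day and have enough drug left may miss those visits: "then they return for the Final Assessment visit, and therefore have fewer total visits". How many would do so cannot be worked out. That passage speaks of 10–15 days on the maximal dose, while the Stage 2 dose escalation text has 28 ± 4 days. These subjects would also have dosed on arrival once already, at Visit 3 or 7.

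The C.4 sentence is weak evidence. It may mean only that the morning dose is not skipped, which fits dosing on arrival. Read with the before-breakfast rule in the same section it leans towards home dosing, but it is at most supporting.

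A reader might infer that the planned vital-sign comparisons or the tremor analysis are compromised. The documents do not support this. The Data Analysis Plan does not say which same-day reading enters the paired or crossover comparison. Nor is the pre-dose value drug-free at these visits, given twice-daily dosing and the oral half-life of 2–5 days cited in section III. Nor should the C.4 warning about low blood pressure with rotigotine be pressed here: it concerns raised drug levels, not a change within hours of a dose.

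**Conclusion.** The contradiction is real, is in the current text, and occurs at every visit with 1- and 3-hour checks: 1 in Stage 1 and 4 in Stage 2. It covers 210 planned visits for 10 + 50 completers, 110 of them on active drug. That is the extent of the conflicting instruction, not an estimate of lost data. The loss lies anywhere from none to all of those visits, depending on an unknown share dosed at home, and is probably nearer the low end if sites follow the visit text.

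The consequence is limited to same-day safety monitoring around the dose and to the timing of the 3-hour sample. First-dose checks at baseline and Visit 6 are untouched. It would go too far to say that the protocol as a whole instructs home dosing, or that any efficacy estimate or planned test is biased. The point is minor, but the schedule is wrong as written and should be corrected.

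**What to change.** 1. In the dosage rows, at Stage 1 Visit 3 and Stage 2 Visits 3, 5, 7 and 9, replace the parenthesis with: *hold the morning dose; take on arrival in clinic after pre-dose vital signs and orthostatic blood pressures*.
2. Clarify the C.4 sentence so that it says the morning dose on these days is taken in clinic.
3. Add *do not take the dose at home* to the day-before reminder call. The call is already scheduled before each of the five visits (Stage 1 call 6; Stage 2 calls 2, 8, 12 and 18), and it also reaches subjects who miss Visit 4 or 8.
4. Optionally, add the same words to the Visit 6 text.

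The cost is five cells, one sentence and one line in a call script, with one further sentence if item 4 is adopted. No visit, procedure or analysis changes.
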